We will also recruit via targeted clinical recruitment in the EPIC electronic health records system by working with an internal EPIC specialist to create a list of candidate participants based on ICD-9/10 codes from NUNM electronic health records. Similarly, our OHSU collaborator will use the Data Warehouse resource of the Oregon Clinical and Translational Research Institute (OCTRI) to identify potential candidates from OHSU's EPIC database. Upon creation of a candidate list, IRB-approved study materials, i.e., an invitation letter and a copy of the flyer, will be mailed to them. They will not be re-contacted if they do not respond to an initial invitation. We will present at medical conferences and have flyers available for conference participants. Additional retention strategies include the use of stipends dispensed for clinical screening (\$50) and each clinical visit completed (\$190 each) following enrollment for up to a total of \$1,000. Additional compensation (\$200) will be provided in the event that closure of campus (e.g. due to COVID-19) requires the participant to go to Quest Diagnostics' phlebotomy clinic for their required blood draw. Participants may be reimbursed for travel and/or lodging expenses if travel cost is a barrier to participation.

Planned						
Table 3 Racial			Ethnic Categorie	S		
Categories	Not Hispanic o		 	Hispanic or Latino		
	Female	Male	Female	Male		
American	0	0	0	0	0	
Indian/Alaska						
Native						
Asian	1	1	0	0	2	
Native	0	0	0	0	0	
Hawaiian or						
Other Pacific						
Islander						
Black or	2	2	1	1	6	
African						
American						
White	11	10	2	1	24	
Total	14	13	3	2	32	

Inclusion Enrollment

This study will enroll biologically male and female participants and therefore will include women. We aim to recruit a sample that is 50% male and 50% female in order to maximize the generalizability of our findings to both men and women. Furthermore, Inflammatory Bowel Disease (IBD) is more common in females (relative risk: 1.53 compared to males) and therefore we are confident women will be well represented.

Protocol

This study will recruit generally from the Oregon and Washington region. Based on the 2016 census, the ethnic distribution of the Portland, OR area is: Caucasian 70%, Hispanic/Latino 10%, Asian 8%, Black 6%, Pacific Islander 1%, Native American 0%, and Other 0%. Participants who come from beyond the immediate area may be compensated for travel and lodging expenses if it is a limiting factor.

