Because Black/African Americans are under-represented in the Portland metro area, we will specifically target recruitment strategies to reach Black/African Americans in the region.

No NIH-defined children will be enrolled.

Assignment of interventions (for controlled trials) Allocation

16a Sequence generation

Randomization will occur in up to 8 blocks of 4 based on biological sex. Initial randomization series will be generated using readily available random sequence generators designed to do so such as Randomization.com, which allows for block randomization.

16 b Allocation Concealment mechanism

Envelopes will be opaque and signed across the seal. The randomization "code" will be kept in a password protected folder that will only be accessible by NUNM's Information Technology staff.

16c Implementation

Masking will be accomplished by: using trained staff not involved in trial operations to: 1. Produce the "code" (e.g., X2=XN and Y1=Placebo); 2. Label XN and placebo bottles generically as "X2" and "Y1"; 3. Generating the blocked randomization sequence using Randomization.com; 4. Create 32 sequentially-numbered, sealed envelopes that contain the random group assignments. Upon confirmation of eligibility and interest, Study Coordinators involved with trial operations will then open the next sequential envelope in the stack at the time of randomization, the envelope number will be recorded, and allocation disclosed to both participant and coordinator at that time as simply "X2" or "Y1", indicating which bottles will be dispensed.

17a Blinding (masking)

Triple-masked without PI, Study Coordinator, or Participant knowing participants' allocation assignment.

17b Un-blinding/masking

Un-blinding is permissible if the Data Safety Monitoring Board requires it upon review and in the case of a Serious Adverse Event (SAE).

Data collection, management, and analysis

18a Data collection methods

1. Adverse Events Report Form

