Adverse event (AE) monitoring will occur using a standardized multi-system AE questionnaire based on the National Cancer Institute's Common Terminology Criteria for Adverse Events v4.0 (2009). The Multi-System Adverse Event questionnaire will be administered at each bi-weekly study visit. However, an AE can also be reported to the study staff at any time and collected via a "Standardized Adverse Events Questionnaire: Spontaneous Reporting" form. The "Spontaneous Reporting" form captures the source of the AE report, the severity/grade of the report, any clinical actions taken, and the current state of the AE. Following a spontaneous report, the study team, sometimes in coordination with a participant's physician, will develop a response plan, which is then also documented.

2. Disease Activity Scale: CDAI

Disease activity will be determined using the CDAI. Relevant components of the CDAI will be collected initially at the Screening visit. Abdominal examination will be performed by a clinical investigator at each visit as outlined in Table 2. If an abdominal exam is unable to be performed, the value for this variable may be gleaned from medical records or derived from participant-reported medical history.

The index consists of eight factors, each summed after adjustment with a weighting factor. The components of the CDAI and weighting factors are the following:

Crohn's Disease Activity Index (CDAI) Questionnaire				
Clinical or laboratory variable	Weighting factor			
Number of liquid or soft stools each day for seven days	x2			
Abdominal pain (graded from 0-3 on severity) each day for seven days	x5			
General wellbeing, subjectively assessed from 0 (well) to 4 (terrible) each day for seven days	x7			
Presence of complications in past seven days	x20			
Taking Lomotil or opiates for diarrhea	x30			
Presence of an abdominal mass (0 as none, 2 as questionable, 5 as definite)	x10			
Percentage deviation from hematocrit of <47% in men and <42% in women	x6			
Percentage deviation from standard weight	x1			

Specific complications that influence score include any of the following, weighted equally: 1) arthritis or arthralgia; 2) iritis or uveitis; 3) erythema nodosum, pyoderma gangrenosum, or aphthous stomatitis; 4) anal fissure, fistula, or abscess; 5) other fistula; 6) temperature over 100F; all within in the last 7 days.

Remission of Crohn's disease is defined as CDAI below 150 with severe disease defined as a value of greater than 450.^{17,18}

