Laboratory measures (including red blood cell count, white blood cell count, hematocrit (%), hemoglobin, mean corpuscular volume, AST, ALT, creatinine-estimated glomerular filtration rate (eGFR), blood urea nitrogen (BUN), and creatinine) will be analyzed by first assessing descriptive statistics including mean, median and standard deviation. All distributions will be tested for skew and transformed (e.g., natural log transformed) as needed to reduce the influence of skew in subsequent analyses. All parameters will be evaluated by formally comparing means from baseline

Protocol

to each time point by unpaired, 2-sided t-tests, as well as for trends over time by applying linear mixed ANOVA models with time point as a repeated factor.

As an element of the evaluation for safety of the intervention, the % laboratory newly abnormal (for values within the clinically normal range at baseline) per clinical laboratory reference ranges for each lab parameter will be reported at each 2-week time point and the % compared between XN and placebo groups by Fisher's exact test.

Assessment for changes in the distribution of each lab parameter will be performed by presenting means and confidence intervals (CI) for the change in each group, as well as the mean CI for the difference between groups; significance will be tested using 2-sided, unpaired t-tests (or, if inspection of distributions indicates strong non-normality, with a non-parametric Wilcoxon signed rank test) of the mean values for XN compared to placebo.

Assessment for overall *increases* or *decreases* in parameters of interest will be tested for linear trends of the means by linear mixed ANOVA with time point as a repeated factor, which may be suggestive of evidence for cumulative toxicity if trending in a clinical deleterious direction.

Analysis of inflammatory cytokines, gut permeability biomarkers, and endotoxemia:

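### Arms are blocked on sex, but the t-tests of mean laboratory values in 20a use neither sex nor the Week 0 value; this costs power if raw visit values are tested and almost nothing if changes are

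*Protocol*

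**What the plan says.** **Design.** Protocol 16a: "Randomization will occur in up to 8 blocks of 4 based on biological sex". Section 15 on recruitment: "We aim to recruit a sample that is 50% male and 50% female". Section 16c describes the allocation material as one series: "Create 32 sequentially-numbered, sealed envelopes that contain the random group assignments".

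**Analysis.** In 20a, under laboratory toxicology measures, one sentence does two things. It describes the presentation as "presenting means and confidence intervals (CI) for the change in each group", together with an interval for the difference between groups. It then says "significance will be tested using 2-sided, unpaired t-tests" (or a rank test if the data are strongly non-normal) "of the mean values for XN compared to placebo". A separate paragraph looks for trends "by linear mixed ANOVA with time point as a repeated factor, which may be suggestive of evidence for cumulative toxicity". Neither names sex or the baseline laboratory value as a covariate.

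**Where adjustment does appear.** Section 20b allows ANCOVA on baseline CDAI, only if the arms differ on CDAI, and the parameters it lists are cytokines, permeability markers and endotoxemia markers. Sex enters a model only in the exploratory longitudinal regressions in 20a.

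**Evidence that a safety measure depends on sex.** The CDAI table in 18a scores "Percentage deviation from hematocrit of <47% in men and <42% in women". Hematocrit is among the laboratory measures listed in 20a, and the CBC is part of the primary safety outcome in section 12.

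**The concern.** When sex is balanced across arms by design, it cannot contribute to the difference between arms. An unadjusted t-test on values nevertheless leaves the whole male-female spread in its standard error. The interval is then too wide and the test rejects less often than its nominal 5%. For an efficacy endpoint that would be merely cautious. For a safety comparison it is the unfavourable direction, because a real fall in hematocrit is more easily reported as no significant difference. Section 6a already cites the absence of significant differences in mean laboratory values as Phase 1 safety evidence, so the same kind of statement may be made from this trial.

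Whether the loss occurs depends on something 20a does not fix: whether the tested quantity is the value at a visit or the change from Week 0.

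**Working it through.** The Protocol states no power or precision figure for mean laboratory values, so there is none to reproduce.

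**Inputs from the Protocol**
- 12 per arm (section 14). 32 randomised less 25% attrition gives 24 in total.
- Sexes 50:50 (section 15), blocked by sex (16a), hence 6 men and 6 women per arm.
- Sex gap in hematocrit: 47 - 42 = 5 points (18a).

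**Assumptions, because the Protocol gives no figure**
- Within-sex SD of 3, 4 or 5 points.
- A 4-point fall on XN as the effect to detect.
- Correlation between Week 0 and follow-up of 0.5 to 0.9 where change or baseline adjustment is considered.

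**Case A: raw values at a visit**

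Share of variance due to sex = 2.5² / (2.5² + SD²):
- SD 3: 6.25/15.25 = 41%
- SD 4: 6.25/22.25 = 28%
- SD 5: 6.25/31.25 = 20%

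Within an arm of 12, the sex gap adds 12 × 2.5² = 75 to the sum of squares, or 75/11 = 6.82 to the variance estimate. So the SE of the arm difference is:
- without sex: √[(SD² + 6.82) × 2/12]
- with sex: SD × √(2/12)

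For SD 4 this gives √(22.82/6) = 1.95 and 4 × 0.408 = 1.63. Averages over simulated trials (at least 20,000 per setting, sex balanced within arm) lie just below these:

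| Within-sex SD | SE, t-test | SE, with sex | True size of nominal 5% t-test | Power for 4-point fall, t-test | Power, with sex |
|---|---|---|---|---|---|
| 3 | 1.61 | 1.21 | about 1% | 69% | 87% |
| 4 | 1.93 | 1.61 | about 2% | 50% | 65% |
| 5 | 2.28 | 2.02 | about 3% | 37% | 46% |

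The power difference is 18, 15 and 9 points. With sex in the model the size is about 5%.

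Interval half-widths use t = 2.074 (22 df) and 2.080 (21 df):
- SD 3: 3.34 against 2.52, 33% wider
- SD 4: 4.00 against 3.35, 20% wider
- SD 5: 4.73 against 4.20, 13% wider

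**Case B: change from Week 0**

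A constant male-female gap cancels within each person. With a gap of 1.5 within-sex SDs and correlations of 0.5 to 0.9, the ratio of interval widths without and with sex is about 0.998, size is about 5%, and power is the same either way. If the change itself differs by sex by 0.3 SD, intervals are 1% to 6% wider and power falls by about 1 point.

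**Case C: the Week 0 value as covariate**

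At SD 4 on raw values, adding sex alone gives about 65% power. Adding the Week 0 value alone gives 78% to 79% at correlation 0.6, and 96% to 97% at 0.8. Adding sex to that brings the first to about 81% and leaves the second unchanged. The Week 0 value is therefore the more useful covariate, and sex is a small addition to it.

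**The case against.** The strongest reply is that the plan means change. The t-test stands in a sentence about changes, with intervals for change. Section 11b lists mean changes among the safety measures, and section 12 interprets laboratory values by new abnormality and change since baseline. On that reading Case B applies and sex adds nothing. This carries weight, and it is why the point is conditional. It does not close the matter: the tested quantity is still worded as mean values of XN against placebo, and an earlier sentence in 20a compares means from baseline to each time point by unpaired tests, which does not describe within-person change either.

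A reader might go further and infer three things that the document does not support.

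- *That the primary comparison is insensitive to toxicity.* Aim 1 in section 7 and the sample size in section 14 concern proportions with an adverse event or abnormal laboratory value. Newly abnormal values are compared by Fisher's test, and a clinical investigator reviews every participant's results (section 12). None of this is affected in the way shown above. The Phase 1 anemia in section 6a was an individual value meeting halting criteria, which these routes are built to catch.
- *That the mixed ANOVA suffers the same loss.* As described, it tests trends over time, a within-person contrast. A constant sex difference does not enter that error.
- *That the t-test is certain to run below 5%.* This requires sex to be balanced among those analysed. Section 16c describes a single envelope series, without separate male and female stacks. If sex is not actually stratified, the raw-value t-test keeps about its nominal size and only precision is lost.

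It is also fair to say that 47% and 42% are scoring references, not group means in this population, and that hematocrit is the only measure for which the Protocol itself shows a sex gap.

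**Conclusion.** The point holds in conditional form. The randomisation factor and the Week 0 value are both absent from the between-arm tests of mean laboratory values, and 20a leaves open whether values or changes are tested.

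- **If raw visit values are tested:** moderate. The size is that of Case A for hematocrit. It rests on the 5-point gap, the assumed SDs, 12 per arm and, for the reduced test size, on sex being balanced as planned. Omitting the Week 0 value costs more than omitting sex.
- **If only changes are tested:** minor. The loss from omitting sex is near nil, and what remains is a wording correction.

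**What to change.** In 20a, state which quantity is compared. For each continuous laboratory parameter, replace the two-sample t-test by a linear model of the visit value on arm, Week 0 value and biological sex, and report the adjusted arm difference with its 95% CI. Keep the unadjusted difference in change as a supporting line. Include sex in any mixed model that compares arms and in any ANCOVA run under 20b.

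The cost is one or two sentences and two degrees of freedom per model. Sex is already recorded for randomisation and the Week 0 laboratory values are already collected, so no new data are needed.

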A sample size of 12 per group provides 80% power to detect a 50% difference in proportions of participants between groups by chi2 test experiencing a laboratory abnormality or adverse event at a significance threshold of α =0.05. In addition, based on our preliminary trial data for change in TNF- α , and applying a 2-sided t-test of means, n=24 allows for n=12 per arm and provides >90% power, at a significance threshold α =0.05, to detect a mean change of -0.5 =/- 0.25 pg/ml in XN-treated participants with CD, based on an estimated mean change of 0.1 +/- 0.25 pg/ml from placebo. Will we randomize up to 32 participants to allow for attrition up to 25% [resulting in a final sample of at least n=24/arm.

Based on our preliminary trial data for change in TNF- α , and applying a 2-sided t-test of means, n=24 allows for n=12 per arm and provides >90% power, at a significance threshold α =0.05, to detect a mean change of -0.5 =/- 0.25 pg/ml in XN-treated participants with CD, based on an estimated mean change of 0.1 +/- 0.25 pg/ml from placebo. Will we randomize up to 32 participants to allow for attrition up to 25% [though we had <10% attrition in our previous trial in this population] resulting in a final sample of at least n=24/arm.

15 Recruitment

Participants will be recruited from the region via posted fliers and the NUNM clinic via posted fliers and IRB-approved mailings to current patients. Members of the study team will present information about study participation to CD support and community groups and set out flyers for attendees to pick up. In addition, we will use Craigslist and social media (i.e. Facebook and Instagram) as well as the NUNM weekly newsletter. Candidates from the community would

simply respond to a dedicated study telephone line or email, and express their interest, and are then contacted by a Study Coordinator.

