Given the small sample size of these clinical trials, results related to changes in inflammatory cytokines (IL-1 β , IL-2, IL-6, IL-8, IL-10, TNF- α , and IL-12p70), gut permeability biomarkers (CD14, intestinal fatty acid binding protein) and markers of endotoxemia (LPS, LPS-binding protein) are considered preliminary, and thus our principle assessment will be measurement of effect size as *Cohen's d* statistic between XN- and placebo-treated groups at each 2-week interval compared to baseline, with the primary comparison being between baseline and week 8. We will also perform formal statistical comparisons as unpaired, 2-sided t-tests (or, if inspection of distributions indicates strong non-normality, with a non-parametric Wilcoxon signed rank test) of the means at relevant time points. The following findings will be considered evidence of possible effects: 1. Clinically and statistically significant effects for changes in cytokines of interest and/or 2. Calculation of a Cohen's d value for effect size estimation greater than 0.5 (with larger d indicating a larger potential effect size).

Assessment for overall *increases* or *decreases* in parameters of interest will be tested for linear trends of the means by linear mixed ANOVA with time point as a repeated factor. Trends will be considered significant if p<0.05 for the model overall.

Analysis of XN, its metabolites, and BAs to determine a small molecule signature of longer-term oral treatment with XN:

We will identify and quantify XN and XN-derived metabolites in plasma, stool, and urine samples. Bile acid profiles will also be determined in the stool samples. The metabolite profile data will then be used for correlation with the time-resolved gut microbiome analysis. This approach will allow us to determine links between metabolite profiles and gut microbiome compositions.

Protocol

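### Cohen's d, the principal assessment of 11 concentration markers, has no stated scale or skew provision; on raw change it would understate proportional effects in skewed markers

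*Protocol*

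**What the plan says.** Protocol section 20a has a separate part for inflammatory cytokines, gut permeability biomarkers and endotoxemia. It names 7 + 2 + 2 = 11 markers and makes Cohen's d the main result: "our principle assessment will be measurement of effect size as *Cohen's d* statistic between XN- and placebo-treated groups at each 2-week interval", relative to baseline, "with the primary comparison being between baseline and week 8". One of two criteria for a possible effect, joined by and/or, is "Calculation of a Cohen's d value for effect size estimation greater than 0.5". The other is a clinically and statistically significant change.

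The formal comparison is an unpaired two-sided t-test or, "if inspection of distributions indicates strong non-normality, with a non-parametric Wilcoxon signed rank test". That is the only provision for non-normality in this part.

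A transformation rule does exist in 20a, but in the preceding part on laboratory toxicology measures, directly after a list of blood-count, liver and renal parameters: "All distributions will be tested for skew and transformed (e.g., natural log transformed) as needed to reduce the influence of skew in subsequent analyses". None of the 11 markers is on that list, and the marker part does not repeat the rule.

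Section 14 states its TNF-α assumption as changes in pg/ml, "applying a 2-sided t-test of means".

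**The concern.** A threshold of d above 0.5 has a fixed meaning only once the scale of the measurement is fixed. The markers are positive concentrations, and such data are often right-skewed. If a treatment lowers such a marker by a proportion, the absolute change depends on where each participant started. A few high values then enlarge the SD of raw change, and d shrinks although the proportional effect is the same.

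The stated remedy does not reach this problem, for three reasons. First, it replaces the p-value and leaves d, the principal statistic, untouched. Second, the signed rank test is for paired data, whereas the comparison described is between independent arms. Third, it is triggered by inspection, marker by marker, which 12 values per arm support poorly.

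At stake is whether the headline result for these markers reflects the treatment effect or the skew of the assay values.

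**Working it through.** **1. The plan's own figure.** Section 14 says "n=24 allows for n=12 per arm and provides >90% power". The inputs are a TNF-α change of -0.5 on XN and 0.1 on placebo, SD 0.25 in each arm, two-sided α = 0.05. Then d = (0.1 + 0.5)/0.25 = 2.4, and the noncentrality is 2.4 × √(12/2) = 5.88 on 22 degrees of freedom. Power is 99.99%, which agrees with the stated figure. The attrition step also reproduces: 24/(1 - 0.25) = 32. These figures are on the raw scale and concern one marker. They say nothing about skew.

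**2. Inputs for the scale comparison.** From the protocol: 12 per arm, change from baseline to week 8, threshold d > 0.5. Assumed, because the documents give no values: lognormal baseline and week-8 values, SD *s* of the log values from 0.3 to 1.0, and correlation *r* of the logs from 0.6 to 0.8.

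**3. Formulas.** d = difference in mean change / pooled SD of change. SD of log change = s√(2(1 - r)). The true effect is set at 1.2 SD of log change, so that log-scale power is 80%. There were 20,000 simulated trials per cell. d is counted in the favourable direction, and ranges run over r = 0.6 to 0.8.

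| Scale, log-SD | Median d | Chance d > 0.5 | t-test power | Rank-sum power on raw change |
|---|---|---|---|---|
| Log, any | 1.21 | 96% | 80% | – |
| Raw, 0.3 | 1.06-1.09 | 91-92% | 70-71% | 68-69% |
| Raw, 0.5 | 0.94-0.97 | 85-87% | 59-61% | 61-63% |
| Raw, 0.8 | 0.77-0.81 | 74-76% | 42-45% | 52-55% |
| Raw, 1.0 | 0.68-0.70 | 67-69% | 33-35% | 47-51% |

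The last column uses the rank-sum test, which suits independent arms, in place of the signed rank test that the protocol names. It recovers part of the lost power at high skew and hardly any at low skew.

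**4. The same comparison with the proportional effect held fixed.** A constant 1.2 SD is a different week-8 ratio in each row. At s = 0.5, r = 0.8 it is exp(-1.2 × 0.5 × √0.4) = 0.68. At s = 1.0, r = 0.6 it is exp(-1.2 × 1.0 × √0.8) = 0.34. With the true effect fixed at a 50% reduction and r = 0.7, the results are:

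| Log-SD | Median d, log | Median d, raw | d > 0.5, log | d > 0.5, raw |
|---|---|---|---|---|
| 0.5 | 1.80 | 1.26 | >99% | 96% |
| 0.8 | 1.14 | 0.75 | 93% | 72% |
| 1.0 | 0.91 | 0.58 | 83% | 58% |
| 1.3 | 0.70 | 0.44 | 68% | 43% |

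At log-SD 0.3 a 50% reduction passes 0.5 in more than 99% of trials on either scale.

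**5. False signals.** With no effect, d exceeds 0.5 in the favourable direction in about 12% of trials per marker on either scale. The log scale therefore does not gain by raising more false flags.

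**6. The inspection step.** With 12 lognormal values, a formal Shapiro-Wilk test at 0.05 detects non-normality in only about 30% of samples at log-SD 0.5 and 57% at 0.8. Inspection by eye is unlikely to be more dependable.

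**The case against.** **The scale is inferred.** The protocol never says that d uses untransformed values. The toxicology rule speaks of all distributions and of subsequent analyses, so it can be read to reach the markers. A reader might infer from the marker text that the protocol prescribes raw-scale d. It does not; it is silent. What stands is that the rule sits under another heading, that the marker part restates the t-test, the Wilcoxon fallback and the mixed model without it, and that section 14 works in pg/ml. Raw change is the natural reading, not a stated one.

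**The scale could be left to the statistical analysis plan.** That is fair for most detail. Here, though, section 20a already fixes the statistic, the contrast, the evidence threshold and the fallback test, and that fallback does not suit the comparison. It leaves open only what gives the threshold its meaning.

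**Effects would not simply be missed.** A reader might also conclude that real effects will go undetected. The figures do not support that. In every row of the first table, median raw d stays above 0.5 and the threshold is passed in 67-92% of trials. Significance is a second route to the same conclusion, and a rank-sum test would recover part of the power. The effect is attenuated, and how much depends on the skew.

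**The simulation favours the fix.** A lognormal marker makes the log scale right by construction, and no skew or correlation comes from the documents. This stands, and the sizes are conditional on it. The only marker figures in the protocol, for TNF-α, imply d = 2.4 on the raw scale.

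**The stakes are limited.** The protocol says that results for cytokines, permeability biomarkers and "markers of endotoxemia (LPS, LPS-binding protein) are considered preliminary". The primary outcome is safety.

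**Conclusion.** The point holds as a gap in scale and skew handling for a principal statistic, together with a fallback test that does not suit independent arms and cannot alter d. It does not hold as a claim that the protocol prescribes untransformed analysis or that real effects will be missed.

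If d is computed on raw change and a marker is lognormal, a true log-scale d of 1.2 appears as about 1.06-1.09 at log-SD 0.3 and about 0.7 at log-SD 1.0. The chance of passing 0.5 drops by 4-5 percentage points at the low end and by about 28 at the high end. The direction is secure for right-skewed markers with proportional effects. The size rests on assumed skew, correlation and effect. Priority is modest: the outcomes are preliminary and not primary, but d is their headline result and the correction is cheap.

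**What to change.** In the marker part of section 20a:

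- State that the 11 markers are analysed as natural logs. Compute Cohen's d and the unpaired between-arm test on log change from baseline, and report the XN:placebo ratio with its confidence interval.
- Replace the inspection-triggered signed rank test with a between-arm rank-sum test, prespecified as a sensitivity analysis for every marker.

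This takes about two sentences and changes no data collection. It has two costs. Logs need one fixed rule for values below the detection limit, set before unmasking. The TNF-α assumption in section 14 should be restated on the log scale or labelled as a raw-scale figure that does not match the analysis scale.
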